13. DEFINITIONS OF SAFETY ANALYSIS TABLES, LISTINGS AND FIGURES

13.1. ADVERSE EVENTS

13.1.1. Treatment-Emergent Principle

All adverse events starting on or after first dosing are considered treatment-emergent adverse events (TEAE).

Adverse events will be placed into analysis periods according to their start date(time). Analysis periods: see section 4.2. The AE will only be presented in the analysis period during which it started. Rule: period start date(time) \leq AE start date(time) \leq period end date(time).

In case the AE start date(time) is incomplete, a worst-case allocation will be done according to the available parts of the AE start date(time), i.e. the AE will be allocated to the treatment period. If the AE start date is equal to the date of the turning point between the screening and treatment analysis periods, and no AE start time is available, then the AE will be allocated to the treatment period. This is considered a worst-case allocation.

All adverse events emerging during the screening period will only be listed, not presented in any of the tables. These events are not TEAEs. All tables will present TEAEs only.

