9.2. INTENSITY OF ADVERSE EVENT

Each AE must be rated on a 3-point scale of increasing intensity:

- **Mild:**
Transient or mild discomfort; no limitation in activity; no medical intervention/therapy required.

- **Moderate:**
Mild to moderate limitation in activity; some assistance may be needed; no or minimal medical intervention/therapy required.
- **Severe:**
Marked limitation in activity; some assistance usually required; medical intervention/therapy required, hospitalization possible.

If there is a change in intensity of an AE, it must be recorded as a separate event.

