9.6. RECORDING ADVERSE EVENTS

Adverse events will be recorded from the signature of the ICF until the final follow-up visit. In case an AE is ongoing at that time, it will be followed up as much as possible by the investigator until resolution or until stabilization.

It is the responsibility of the investigator to collect all AEs (both serious and non-serious) derived by spontaneous, unsolicited reports of subjects, by observation and by routine open questioning (such as “How do you feel?”).

Any adverse or unusual event occurring during or after the clinical study (until the follow-up visit), whether observed by the investigator or investigational staff, or spontaneously reported by the subjects, will be recorded in the eCRF and medical file.

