13.1.3. Worst-Case Principle

When cross-tabulating AE preferred terms versus an AE attribute (e.g., intensity), the worst-case is always applied within each analysis period. I.e., when a subject has multiple times the same AE preferred term in the same analysis period, then the subject is reported only once: only with the worst intensity. If this happens in two different analysis periods, the AE is reported twice: once in each analysis period.

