13.1.6. Tables

No formal inferential statistics (p-values) will be derived.

Analysis periods will be replaced by their respective treatment via the data captured in the CRF (i.e. an as-treated allocation). All tabulations and listings will present treatments rather than analysis periods.

Table 14.3.1.1: Treatment-emergent adverse events: Summary table

Tabulation per treatment of the number and percentage of subjects with the following:

- Subjects with at least one treatment-emergent adverse event (TEAE)
- Subjects with at least one serious TEAE
- Subjects who died
- Subjects with at least one mild TEAE as worst intensity
- Subjects with at least one moderate TEAE as worst intensity
- Subjects with at least one severe TEAE
- Subjects with at least one TEAE that was considered treatment-related
- Subjects with at least one TEAE for which the study treatment was temporarily stopped
- Subjects with at least one TEAE for which the study treatment was permanently stopped.

Population: safety population.

Table 14.3.1.2: Treatment-emergent adverse events: Tabulation of all adverse events

Tabulation of TEAE preferred terms per body class, per treatment group.

With a frequency tabulation of the number of events (reportings).

Population: safety.

Table 14.3.1.3: Treatment-emergent adverse events: Tabulation per intensity

Cross-tabulation of TEAE preferred terms versus their intensity. Use the worst-case intensity per TEAE per subject. Per treatment group.

Population: safety.

Table 14.3.1.4: Treatment-emergent adverse events: Tabulation of all treatment-related events

Tabulation of TEAE preferred terms per body class, per treatment group. Selecting only the TEAEs that were treatment-related (see section 13.1.2).

Population: safety.

Table 14.3.1.5: Treatment-emergent adverse events: Tabulation of the intensity of treatment-related events

Cross-tabulation per analysis period of TEAE preferred terms versus their intensity; per body class and per treatment group. Use the worst-case intensity per TEAE per subject, selecting only the TEAEs that were treatment-related (see section 13.1.2).

Population: safety.

Table 14.3.1.6: Serious treatment-emergent adverse events: Tabulation for EudraCT reporting

Tabulation of the number of subjects and events per body class, preferred term and per treatment.

Population: Safety.

Table 14.3.1.7: Non-serious treatment-emergent adverse events: Tabulation for EudraCT reporting

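### A screening adverse event that only eases after first dose can be tabulated as treatment-emergent, and intensity changes multiply event totals but not subject counts

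*SAP*

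**What the plan says.** Four rules act together.

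- **Recording.** Protocol 9.2: "If there is a change in intensity of an AE, it must be recorded as a separate event". The rule is mandatory and covers decreases as well as increases.
- **Collection window.** Protocol 9.6: "Adverse events will be recorded from the signature of the ICF until the final follow-up visit". Screening lasts up to 28 days, so events can already be open at first dose.
- **Classification.** SAP 13.1.1: "All adverse events starting on or after first dosing are considered treatment-emergent adverse events (TEAE". Allocation to a period also goes by start: "The AE will only be presented in the analysis period during which it started". The section sets no condition on worsening, makes no comparison with the pre-dose state and has no link to an earlier record of the same event.
- **Screening events.** The same section says: "All adverse events emerging during the screening period will only be listed, not presented in any of the tables". It adds that these events are not TEAEs.

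For counting, Table 14.3.1.2 (SAP 13.1.6) is specified as "With a frequency tabulation of the number of events (reportings". Table 14.3.1.6, for serious TEAEs, is specified as "Tabulation of the number of subjects and events per body class, preferred term and per treatment", and Tables 14.3.1.7 and 14.3.1.8 follow the same layout for non-serious TEAEs. When a subject has the same preferred term more than once in a period, SAP 13.1.3 says of the attribute cross-tabulations: "then the subject is reported only once: only with the worst intensity".

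**The concern.** The protocol splits one clinical episode into several records, and the SAP treats each record as an event in its own right. For an episode that straddles first dose, the later record loses its screening origin. A cough rated moderate in screening that eases to mild on Day 5 leaves a record starting on Day 5, and by the start-date test that record is a TEAE. The subject improved, yet the table shows an event arising on treatment.

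This matters because AE incidence is the first component of the primary endpoint (Protocol 4.1), and the groups are small enough for one record to move a percentage visibly. The period labelled Treatment in SAP 4.2 runs to study termination, so an improvement during follow-up counts in the same way.

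A second, smaller effect arises on treatment: an episode that fluctuates becomes several entries wherever events, rather than subjects, are counted.

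**Working it through.** The plan states no figure to reproduce. The check applies the two rules literally to example episodes and compares the result with a new-or-worsened definition that links records of one episode.

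**Inputs**
- Group size: 25 subjects per cohort at 2:2:1 (Protocol 5.1) gives 25 × 2/5 = 10 per dose and 25 × 1/5 = 5 on placebo. Placebo is pooled in tables (SAP 3.3), so 5 + 5 = 10.
- Rule A (Protocol 9.2): a new record at each intensity change.
- Rule B (SAP 13.1.1): a record is a TEAE if it starts on or after first dose.
- Assumption: the new record carries the date of the change as its start date. Neither document says so.

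**Step 1: example episodes**

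| Episode | TEAE events as written | Subjects with a TEAE as written | TEAE events if new or worsened, linked |
|---|---|---|---|
| Screening moderate, mild from Day 5 | 1 | 1 | 0 |
| Screening severe, then moderate, then mild after dosing | 2 | 1 | 0 |
| Screening mild, moderate from Day 5 | 1 | 1 | 1 |
| On treatment: mild, moderate, mild | 3 | 1 | 1 |
| On treatment: mild, moderate, severe, moderate, mild | 5 | 1 | 1 |

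The first two rows are the misclassification, and it reaches subject counts. The third row shows that worsening after first dose is already captured. The last two rows follow the formula: k intensity changes give k + 1 events (k = 2 gives 3, k = 4 gives 5) and one subject.

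**Step 2: size of one misclassified record.** In a group of 10, one subject is 1/10 = 10 percentage points. That is the change in the preferred term's incidence if the subject has no other TEAE with that term. It is the change in the overall line for at least one TEAE (Table 14.3.1.1) only if the subject has no other TEAE of any kind.

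**Step 3: how often.** The documents give no rate. If a fraction p of subjects has a screening AE that eases after dosing, the chance of at least one such subject in a group of 10 is 1 − (1 − p)^10. For assumed p of 2%, 5%, 10% and 20%, this is 18%, 40%, 65% and 89%. The range reflects the assumption and is not evidence about this trial.

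**Step 4: does another rule repair it?** SAP 13.1.3 collapses repeats within one analysis period. Across periods it reports the event once in each, so it does not tie a Day 5 record to its screening parent. Within the single post-dose period it does prevent a subject from being counted twice. It does not act on event totals. Durations are derived per record (SAP 13.1.4), but appear only in listings.

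**The case against.** The strongest reply is that the effect is narrow and falls on all arms alike. It needs an event that starts between consent and first dose, is still open at dosing, and later falls in intensity without resolving. Long-standing symptoms need not qualify: conditions still present at study start have their own concomitant-disease listing (SAP 8.6), and unstable pulmonary status requiring a therapy change within 4 weeks before first dose is an exclusion (Protocol 5.2.3). AE tables carry no p-values, the SAP leans to worst-case allocation elsewhere, and the pre-treatment and treatment-emergent listings let a reader trace a split event. The eCRF instructions and mock tables are not in the two documents and may already hold a link between records.

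Most of this stands as a limit on size. It does not remove the contradiction: the SAP says screening events stay out of the tables, and its start-date test lets their continuation in. The worst-case allocations in SAP 13.1.1 and 13.1.2 deal with incomplete dates and missing relatedness, not with events known to have begun before dosing.

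A reader might infer several stronger points that the documents do not support.

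- **Fluctuating episodes inflate AE incidence.** They do not; only event totals grow.
- **One record moves a placebo group by 20 points.** That needs a 5-subject denominator. Tables pool placebo, and no AE table specifies a split by cohort.
- **The misclassified record is notable because it passes the 5% cut of Table 14.3.1.8.** Any single event in a group of 10 does.
- **The serious-event table is inflated generally.** Table 14.3.1.6 is touched only if a serious AE is itself split.
- **Worsening after first dose is missed.** The existing rules already capture it.
- **One arm is favoured by design.** The same rule applies to every arm, so the main effect is noise, unless the drug itself changes AE intensity.

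**Conclusion.** The point holds in a limited form. Followed as written, and on the assumption that a split record starts on the date of the intensity change, the plan counts a screening AE that only improves after first dose as a TEAE, against the SAP's own intent. Each such record is worth up to 10 percentage points in a 10-subject group, under the conditions in step 2. How many will occur cannot be judged from the documents.

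The repeat counting is a separate and lesser matter. It affects the event totals in Tables 14.3.1.2, 14.3.1.7 and 14.3.1.8, those in Table 14.3.1.6 for serious AEs only, and the per-record durations in listings. Because the first effect reaches a component of the primary endpoint and is cheap to remove, the SAP wording should be changed.

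**What to change.** In SAP 13.1.1, define a TEAE as an AE with first onset on or after first dose, or one that worsens after first dose relative to its last pre-dose intensity. State that a record opened only because a pre-dose AE decreased in intensity is not a TEAE.

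For event totals, link the intensity-change records of the same AE and count them as one episode at maximum intensity. Keep every raw record in the listings, so nothing is lost. The link can come from a parent-event number in the eCRF, if there is one or one can be added, or from a rule based on the same preferred term with contiguous dates.

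The cost is SAP wording and programming. The small downside is manual review of the links, since a contiguous-date rule could merge distinct episodes; with about 50 subjects that is manageable. Protocol 9.2 need not change.

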1.3. STUDY DESIGN

This is a Phase IIa, multi-center, randomized, double-blind, placebo-controlled, parallel-group study to evaluate 4 different doses of GLPG2222 administered orally and q.d. for 29 days to adult male and female subjects with a confirmed diagnosis of CF and homozygous for the F508del CFTR mutation. Eligible subjects must be on a stable concomitant medication regimen for at least 4 weeks prior to the first study drug administration and agree to continue the same regimen for the duration of the study.

A schedule of the study design is provided in Figure 1.

[figure not shown]

Figure 1: Study design

The study will consist of a screening period of maximum 4 weeks (starting when the subject has signed the informed consent form [ICF]), a treatment period of 4 weeks, and a follow-up period of 2 weeks. Enrolled subjects will come to the clinical study center at screening, on Day 1 (baseline), Day 15, Day 29, and at the follow-up visit (2 weeks after the last study drug administration).

Approximately 50 evaluable subjects are planned to be included sequentially in the study: the first 25 subjects will be assigned to Cohort A (i.e. subjects 1 to 25) and the next 25 subjects will be assigned to Cohort B (i.e. subjects 26 to 50). Subjects participating in Cohort A are not allowed to participate in Cohort B. In each study cohort, subjects will be randomized in a 2:2:1 ratio to receive:

- Cohort A: 50 mg GLPG2222, 100 mg GLPG2222 or placebo q.d. for 29 days.
- Cohort B: 200 mg GLPG2222, 400 mg GLPG2222 or placebo q.d. for 29 days.

Assessments for efficacy and safety will be performed during the study at the time points specified in the flow chart.

Additionally, subjects can choose to participate in the optional substudy, in which nasal brushings will be collected.

Subjects will be in the study for a duration of minimum 6 weeks and maximum 10 weeks (from screening until the follow-up visit, depending on the duration of the screening period).

The end of the study is defined as the last contact with the last subject.

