4.2. ANALYSIS PERIODS FOR NON-VISIT DATA

These analysis periods are to be used for allocation of events into periods (e.g., adverse events).

Analysis period	Start period	End Period
Screening	Date of signing the ICF, with 00:00 added as time part.	First treatment administration date(time) - 1 minute
Treatment	First treatment administration date(time)	Study termination date, with 23:59 added as time part in case the time part would be missing or incomplete.

Note that the last analysis period in case of early termination will always be ended by the study termination date (date of last contact, with 23:59 added as time part in case the time part would be missing or incomplete).

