5.4.3. Handling of Missing Date(Time) or Partially Known Date(Time)

No imputation will be done of missing date(time) fields, nor of the missing parts of partially known date(time) fields. When needed (e.g., a double phase allocation), a worst-case selection will be made.

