8.7. PRIOR AND CONCOMITANT THERAPIES

8.7.1. Classification of Therapies

All prior and concomitant therapies will be allocated into exactly one of the following categories:

- Prior only: the therapy ended before the first study drug administration.
- Concomitant only: the therapy started on or after the first study drug administration.
- Post-treatment: the therapy started after the last study drug administration.
- Prior and concomitant: the therapy started before the first study drug administration, and ended on or after the first study drug administration.

When the start date is missing, the therapy is assumed to have started on the same day as the first administration of study drug.

When the end date is missing, the therapy is assumed to be still ongoing after the end of the study.

When the start date is only partially known, the missing parts will be imputed by the first day of the month/year, or the day of the first medication intake in case the nonmissing part matches.

When the end date is only partially known, the missing parts will be imputed by the last day of the month/year.

Imputation of start and end dates is only done for the classification into prior / concomitant / prior+concomitant. The listing will present the original start and end dates, also when incomplete. Fields like start and stop days will not be derived from imputed incomplete dates.

No further classification into analysis periods will be done.

The relative study day of therapy start and stop will be derived as follows (only listed):

Start day

= (Therapy start date) – (date of first study medication administration) + 1, when the start date of therapy is known and complete, and when the therapy start date is on or after the date of first study medication;

= (Therapy start date) – (date of first study medication administration), when the start date of therapy is known and complete, and when the therapy start date is before the date of first study medication;

= missing when the start date of therapy is unknown, missing, or incomplete.

Stop day

- = (Therapy stop date) – (date of first study medication administration) + 1, when the end date of therapy is known and complete, and the end date of therapy is on or after the date of first study medication;
- = (Therapy stop date) – (date of first study medication administration), when the end date of therapy is known and complete, and the end date of therapy is before the date of first study medication;

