13.1.4. Adverse Event Onset Day and Duration

AE onset day in the study

$= ((\text{AE start date}) - (\text{date of first study drug administration})) + 1$, when the AE start date is completely known; the “+1” is not needed if the AE start date is before the first study drug administration date;

= missing when the AE start date is incomplete or unknown.

AE onset day in the period

= $((\text{AE start date}) - (\text{start date of the period into which the AE was allocated})) + 1$, when the AE start date is completely known;

= missing when the AE start date is incomplete or unknown.

AE duration

= $((\text{AE stop date}) - (\text{AE start date})) + 1$, when both dates are completely known;

= $((\text{Study termination date}) - (\text{AE start date})) + 1$, when the AE start date is fully known but the AE is not resolved at the end of the study; in this case the duration will be presented as “>x days” in the listing to identify it as a censored result;

= missing when the AE start date is incomplete or unknown, or when the AE has resolved but with an incomplete or unknown end date.

These derived parameters will only be presented in the listings. Note that the start and stop times of the AE are not used; only the dates are used.

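### SAP 13.1.1 ignores the AE stop date when the start date is incomplete, so an event that ended before the first dose can be tabulated as treatment-emergent

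*SAP*

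**What the plan says.** SAP 13.1.1 opens with the definition: "All adverse events starting on or after first dosing are considered treatment-emergent adverse events (TEAE". It places each AE in an analysis period by its start date(time), and says that events arising in screening appear in listings only and that every AE table shows TEAEs only. For an incomplete start date(time) it calls for a worst-case allocation "according to the available parts of the AE start date(time), i.e. the AE will be allocated to the treatment period". A further sentence sends an AE to the treatment period if it starts on the turning-point date between screening and treatment and has no start time.

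SAP 4.2 ends the screening period at "First treatment administration date(time) - 1 minute". SAP 5.4.3 gives the general rule for partial dates, which is no imputation, and adds: "When needed (e.g., a double phase allocation), a worst-case selection will be made". Neither 13.1.1 nor 5.4.3 mentions the AE stop date.

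The stop date is collected. SAP 13.1.4 uses it to derive AE duration, "when both dates are completely known", and shows that duration only in listings. For medications, SAP 8.7.1 does use the end date to classify: "Prior only: the therapy ended before the first study drug administration".

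**The concern.** A worst-case rule is meant for events whose timing cannot be settled. Here it also catches events whose timing is settled by another recorded field. If an AE ended before the first dose, it began before the first dose, however little is known of its start date.

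Such events can arise. Protocol 9.6 states: "Adverse events will be recorded from the signature of the ICF until the final follow-up visit". Screening may last up to 4 weeks (SAP 1.3: "The study will consist of a screening period of maximum 4 weeks"), which leaves room for a short event to begin and resolve before dosing.

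AE incidence is the first-named component of the primary endpoint (Protocol 4.1, SAP 1.2.1). A misallocated event would be counted in the TEAE tables and would be missing from the listing of pre-treatment events (Listing 16.2.10.3). If its causality assessment were also missing, SAP 13.1.2 would make it a treatment-related TEAE, although it ended before exposure.

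**Working it through.** The plan states no figure on this point, so there is none to reproduce. The check applies the rule to example dates and then scales the effect of one event.

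**Step 1: the logic.** For any AE, start ≤ stop. If stop < first dose, then start < first dose, so the AE fails the definition in 13.1.1.

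**Step 2: the rule applied.** The first dose is assumed to be on 20 March 2017; all dates are illustrative. The narrow reading sends an AE to treatment only if the known start parts are compatible with the treatment period. The broad reading sends every AE with an incomplete start there. The last column uses the narrow reading after first checking whether a complete stop date precedes dosing.

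| Start known | Stop known | Narrow reading | Broad reading | With stop-date check |
|---|---|---|---|---|
| March 2017 | 10 March 2017 | treatment | treatment | screening |
| 2017 only | 10 March 2017 | treatment | treatment | screening |
| February 2017 | 10 March 2017 | screening | treatment | screening |
| March 2017 | missing | treatment | treatment | treatment |
| March 2017 | 25 March 2017 | treatment | treatment | treatment |

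The first two rows are misclassified under both readings, so the point does not depend on which was intended. The last two rows show that a stop-date check leaves truly uncertain events in the treatment period.

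**Step 3: size of one event.** Inputs are 25 subjects per cohort, two cohorts, and 2:2:1 randomization (Protocol 5.1).

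- Each dose group: 25 × 2/5 = 10.
- Pooled placebo: 2 × 25 × 1/5 = 10.
- One subject: 1/10 = 10 percentage points.

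The 10-point shift is conditional. On the any-TEAE line it needs a subject with no other TEAE; on a preferred-term line, a subject with no other TEAE of that term. The event count in Table 14.3.1.2 rises by one in any case. Since 10% exceeds the 5% cut-off of Table 14.3.1.8, one non-serious event is enough to bring a term into that table.

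**Step 4: how often.** An affected event needs a partial start date compatible with treatment and stop information that places its end before dosing. The documents give neither frequency, so no expected count can be derived.

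**The case against.** The best defence is that this is an openly declared worst-case convention. It over-counts TEAEs rather than hiding them, it is the same in all arms of a double-blind trial, and the AE tables carry no p-values (SAP 13.1.6). Partial dates should also be uncommon. Subjects keep a diary of emerging AEs from screening (Protocol 5.3.7.1), source notes should hold AE start and end dates (Protocol 11.4), eCRF entries are checked and queried (Protocol 11.5), and participation lasts at most 10 weeks. Listing 16.2.10.1 prints AE dates beside period dates, so a stop date before the period start would be visible.

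This stands as to severity. It does not remove the error: the listing exposes the event but the tables still count it. Over-counting is also not conservative in every arm, because an extra event in pooled placebo raises the comparator rate.

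A reader might infer something stronger: that the clause after the i.e. sends every incomplete start to treatment, including a known month before dosing, or a complete pre-dose date that lacks only a time. The text points the other way. Allocating by the available parts would have no function if the parts never mattered. The turning-point sentence would be redundant if any missing time already meant treatment. SAP 5.4.3 keeps the worst case for when it is needed, and a known earlier month or date leaves nothing to resolve. At most the wording is loose enough for two programmers to code it differently.

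A reader might also see a contradiction with SAP 5.4.3. That section does not mention the stop date. It neither closes the gap nor is contradicted by 13.1.1; the conflict is within 13.1.1 itself.

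**Conclusion.** The rule is wrong as written for one class of event: an AE whose partial start date is compatible with the treatment period but whose known stop date(time) is before the first dose. It is tabulated as a TEAE under either reading of 13.1.1, against that section's own definition and its rule that screening events are only listed.

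The severity is minor. One affected subject shifts an incidence line by 10 percentage points, assuming the planned group sizes of about 10 and no other TEAE for that subject on that line. The documents do not support a claim about how many such events will occur, or that the rule as a whole sweeps clearly pre-dose events into the treatment period. The worst-case principle itself is sound for events whose timing remains unknown.

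**What to change.** Replace the incomplete-date and turning-point sentences in SAP 13.1.1. Adding a sentence beside them would leave competing rules: an AE on the first-dose date with no start time, but with a stop time before dosing, would go to screening under one and to treatment under the other. Suggested text:

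*If the AE start date(time) is incomplete, the AE is allocated to screening when the available start-date parts, or the available parts of the AE stop date(time), establish that it started before the first study drug administration. In all other cases, including a start on the first-dose date with no start time and no stop date(time) shown to be before first dosing, it is allocated to the treatment period (worst case).*

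This covers partial stop dates and keeps the worst case for every event that remains ambiguous. It also settles the loose wording about known earlier months and missing times. The cost is a short SAP edit and one condition in the AE derivation, using a variable already collected. No data collection, table layout or clinical procedure changes. It is best made before unblinding.
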